#### Lost-to-Follow-up

If the subject misses two consecutive scheduled follow-up time points and the attempts at contacting the subject detailed below are unsuccessful, then the subject is considered lost-to-follow-up. Site personnel shall make all reasonable efforts to locate and communicate with the subject (and document these efforts in the source documents), including the following, for each time an attempt was made to contact the subject:

- A minimum of two telephone calls on different days over the specified follow-up windows to contact the subject should be recorded in the source documentation, including date, time and initials of site personnel trying to make contact.
- If these attempts are unsuccessful, a letter should be sent via registered mail to the subject.
- If a subject misses one or more non-consecutive follow-up contact time points, it will be considered a missed visit. The subject may then return for subsequent visits.
- If the subject misses two consecutive time points and the above-mentioned attempts at communicating with the subject are unsuccessful, the subject will be considered lost-to-follow-up.

## Clinical Investigation Plan

**Note:** Telephone contact with the general practitioner, non-clinical investigation cardiologist or relative without the presence of the subject or indirect documentation obtained via discharge letters will not be considered as subject contact.

### 6.0 TREATMENT AND EVALUATION OF ENDPOINTS

The Principal Investigator is responsible for ensuring all clinical investigation data is collected as outlined in this CIP. Unless otherwise noted, it is recommended that the site follow standard of care for any activities not specifically stated in this CIP.

#### 6.1 Baseline Clinical Assessments

The assessments listed below will be collected from each subject at the Baseline Visit. Information gathered at this visit will be used to verify eligibility of the subject for the trial.

- Documentation of the informed consent process as defined in **Section 5.2.2**
- Demographics
- Medical history, cardiac arrhythmia history, and documentation for the diagnosis of persistent AF
- Administration of a 24-hour Holter that must demonstrate 100% continuous AF within 90-days of the procedure OR documentation of 2 ECGs (from any form of rhythm monitoring) taken at least 7-days apart showing continuous AF

NOTE: Repeat Holter assessments are not allowed if 100% continuous AF was not demonstrated on the first 24-hour Holter assessment. If artifact is present in the tracing, it can be disregarded when assessing for 100% continuous AF. All readable portions of the tracing should demonstrate continuous AF (non-sinus rhythm).

- AAD history, including maximum ineffective dosages and dosages not tolerated
  - Intolerance is defined as unable, unwilling, or refusal to take Class I or III AADs
- Anticoagulation drug usage
- Complete physical exam including 12-lead ECG, NYHA assessment, and CHA2DS2VASc score assessment
- Neurological assessment as recommended in the 2017 Consensus Statement
- Echocardiography or CT results or equivalent imaging (LVEF and LA diameter assessments)

## Clinical Investigation Plan

- Thrombus assessment must be performed as specified in **Section 6.2.6**.
- Administration of the EuroQol Five Dimensions Questionnaire (EQ-5D-5L) quality of life questionnaire as defined in **Section 6.7.1**
- Documentation of adverse events and protocol deviations that occur after consent and prior to the procedure

### 6.2 Peri-Procedural Considerations

#### 6.2.1 Anticoagulation

The anticoagulation strategies from the 2017 Expert Consensus Statement on Catheter and Surgical Ablation for AF for pre- and post-ablation are outlined below and are recommended to be followed for management of study subjects. However, **it is strongly recommended that a strategy of uninterrupted anti-coagulation be in place for peri-operative management**. All start and stop times of anticoagulants must be documented for the trial. Subjects who are taking coumadin or warfarin will have international normalized ratio (INR) values documented on the day of the procedure and after the drug is restarted after the ablation procedure.

##### Pre-ablation

- Patients who are therapeutically anticoagulated with warfarin, dabigatran or rivaroxaban prior to the ablation are recommended to have the ablation procedure performed without interruption of the anticoagulant.
- Patients anticoagulated with a novel oral anticoagulant (NOAC) prior to undergoing an AF ablation procedure may have one to two doses of the NOAC withheld prior to AF ablation with re-initiation of the NOAC post-ablation.
- Anticoagulation guidelines that pertain to cardioversion of AF should be adhered to in patients who present for an AF ablation procedure.

##### Post-ablation

- In patients who are not therapeutically anticoagulated prior to catheter ablation of AF and in whom warfarin will be used for anticoagulation post-ablation, low molecular weight heparin or intravenous heparin should be used as a bridge for initiation of systemic anticoagulation with warfarin following AF ablation.
- Systemic anticoagulation with warfarin or NOAC is recommended for at least 2-months post-ablation of AF. Systemic anticoagulation beyond 2-months post-ablation should be based on the patient's stroke risk profile (not on the perceived success or failure of the ablation procedure).
- In patients who have not been anticoagulated prior to catheter ablation of AF or in whom anticoagulation with a NOAC or warfarin has been interrupted prior to ablation, administration of a NOAC 3 to 5 hours after achievement of hemostasis is reasonable post-ablation.

#### 6.2.2 Antiarrhythmic Drug Therapy

The 2017 Consensus Statement on Catheter and Surgical Ablation for Atrial Fibrillation states that AADs need to be discontinued for at least five half-lives and beta-blockers withheld for at least 24-hours prior to the ablation procedure if a strategy searching for non-pulmonary vein triggers is employed. As

## Clinical Investigation Plan

the ablation strategy is left to the discretion of the investigator, other than the requirement for PV isolation, this clinical investigation will not require that all subjects discontinue Class I and III AADs for at least five half-lives. However, AAD usage (start and stop date, time, frequency and dose information) will be documented for the trial prior to and after the subject's procedure(s).

During the blanking period after the ablation procedure, it is recommended that any current AAD medication be continued following the ablation procedure to aid with healing. Current AADs should be withdrawn 4-6 weeks after ablation, unless clinically contraindicated, to assess for recurrence of symptoms and for determination of the need for a repeat ablation during the blanking or therapy consolidation periods. It is recommended that sites phone subjects 4-6 weeks after ablation to remind them to discontinue their AAD medication.

It is recommended that subjects be taken off all Class I and III AADs prescribed for AF/AFL/AT after the blanking and therapy consolidation periods. If the investigator feels that the subject may benefit from a Class I or III AAD during the 9-month evaluation period (post-blanking and therapy consolidation periods), then the investigator should first prescribe a previously ineffective Class I or III AAD up to the historic maximum ineffective dose prior to the ablation procedure. If the historic maximum ineffective dose remains ineffective then a new Class I or III AAD may be initiated.

### 6.2.3 Vascular Access

It is strongly recommended that vascular access be obtained using ultrasound to minimize complications.

### 6.2.4 Esophageal Temperature Monitoring

It is strongly recommended that esophageal temperature be monitored using an esophageal temperature probe at the anatomical location nearest the site of energy delivery. Alternatively, esophageal deviation may be performed when ablating near the esophagus.

Termination of energy is strongly recommended if a  $>1^{\circ}\text{C}$  rise in esophageal temperature is observed.

### 6.2.5 Pregnancy Testing

A urine pregnancy test must be performed for women of child-bearing potential, preferably on the day of the procedure.

### 6.2.6 Thrombus Assessment

Left atrial thrombus assessment by transesophageal echocardiography (TEE) or phased-array intracardiac echocardiography (ICE) must be performed within one day of the ablation procedure or on the day of the procedure.

If a thrombus is discovered within a day of the procedure, the procedure should be postponed, and the subject placed on anticoagulation until the thrombus is resolved and confirmed by imaging. Once confirmation is obtained demonstrating resolution of the thrombus, the inclusion/exclusion criteria should be re-reviewed for the subject to confirm continued eligibility for the trial.

The subject will not need to be re-consented for the trial after the thrombus resolves, provided that the subject meets all eligibility criteria and will undergo an ablation procedure within 90-days of the original consent date unless otherwise indicated by the governing IRB/EC.

## Clinical Investigation Plan

### 6.3 Initial Ablation Procedure

#### 6.3.1 Ablation Procedure

For those subjects meeting eligibility criteria and who are enrolled in the trial, it is preferable that the ablation procedure be performed within 14-days of consent. Any subject who does not meet eligibility requirements will be a screen failure and will be excluded from this trial.

The subject's rhythm when they enter the EP lab will be documented for the trial. All cardioversions that occur from the time the subject enters the lab to the start of the procedure and during the procedure will be documented.

It is recommended that heparin be administered prior to trans-septal puncture during the AF catheter ablation procedure and adjusted to achieve and maintain an ACT of at least 300 seconds. Use of an ICE probe during the procedure to guide septal puncture and to monitor catheter position and manipulation is strongly recommended. Administration of protamine to reverse heparin is acceptable.

Following trans-septal access, a standard treatment scheme for mapping and ablation should be conducted. Use of robotic systems or Stereotaxis to assist with the procedure is not allowed. Physicians performing ablations must be qualified operators and trained on the study. Each physician who ablates during a particular case needs to be documented on the Procedure CRF.

The procedure should be performed according to the TactiCath SE *Instructions for Use* document using the recommended ablation parameters as noted in the document:

- Power (10 - 30W)
- Contact force (target 20 g, 10-30 g)
- Temperature (37 – 50 °C)
- Irrigation flow rate (17 - 30 ml/min)

When ablating near the left atrial posterior wall, it is recommended that a minimum targeted contact force of 5-10 grams be used as specified in the 2017 HRS Consensus Statement. Recommended maximum parameters for ablating the left atrial posterior wall near the esophagus are:

[figure not shown]
- Contact force: ≤15 g for ≤10 seconds
- Power: up to 40W

The ablation strategy outlined in **Figure 5** is recommended for initial ablation of all subjects:

1. Perform wide area circumferential ablation to electrically isolate the pulmonary veins.
2. Administer isoproterenol following initial pulmonary vein isolation if the subject is in sinus rhythm to identify gaps in ablation and to identify and ablate any additional AF triggers.
3. Cardiovert the subject before isoproterenol challenge if he/she is not in sinus rhythm after initial pulmonary vein isolation.
4. Ablation of additional cardiac substrate (e.g. ablation of complex fractionated atrial electrograms (CFAE) or linear ablations) should only be considered if sinus rhythm is not restored after isolation of the pulmonary veins and ablation of non-PV triggers.

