### 6.4 Repeat Ablation Procedures

One ablation procedure for treatment of AF/AT/atypical AFL recurrence is allowed during the blanking and therapy consolidation periods (within 180 days post-initial procedure) using the recommended parameters listed in the TactiCath SE *Instructions for Use* document. Note that recurrence and ablation of typical AFL alone does not count as a repeat procedure for AF recurrence.

Certain assessments need to be performed if a repeat ablation is required. Thrombus assessment must be performed prior to ablating the subject. Verification of the exclusion of pericardial effusion must also be performed prior to the conclusion of the procedure.

A 7-day ( $\pm$  2 days) follow-up phone call or in-person visit to the subject will be conducted after the repeat procedure. All other follow-up visits will occur as previously scheduled from the initial ablation procedure. Note that the 90-day blanking period followed by a 90-day therapy consolidation period are still in place from the initial procedure.

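### Section 6.3.1 attributes a power range of 10-30 W to the Instructions for Use, then gives a maximum of up to 40 W near the esophagus without saying how the two relate

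*Combined protocol and SAP*

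**What the plan says.** Section 6.3.1 (Ablation Procedure) says the procedure should be carried out in line with the TactiCath SE IFU, "using the recommended ablation parameters as noted in the document". The list that follows gives power as 10 to 30 W, together with contact force, temperature and irrigation flow.

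The section then turns to the posterior wall of the left atrium. After a sentence on minimum contact force there, attributed to the 2017 consensus statement, it continues: "Recommended maximum parameters for ablating the left atrial posterior wall near the esophagus are". The bullets under that lead-in are "Contact force: ≤15 g for ≤10 seconds" and "Power: up to 40W".

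Other sections bear on the same point:

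- Section 2.2.1 says all study devices will be used within their indications and IFU.
- Section 3.0 describes the study as using market-approved product within its labeling.
- Section 2.2.5 names approved labeling and published practice guidelines together, without ranking them.
- Section 6.4 allows one repeat ablation "using the recommended parameters listed in the TactiCath SE" IFU. It does not mention the posterior-wall values.

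**The concern.** A limit for one site would normally be read as applying within the general range. Here the ceiling for the named site is higher than the ceiling the plan presents as the IFU's, and the visible text does not say that this is intended. An operator who follows Section 6.3.1 to the letter could use a power inside one list and outside the other. The same operator is told in Sections 2.2.1 and 3.0 that use stays within the IFU or labeling.

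Two things are at stake. The first is safety relevance. This is the one location with its own maximum parameters, and Section 4.1.1 includes atrioesophageal fistula in the primary safety endpoint and evaluates it through 15 months. That endpoint counts the initial procedure and any repeat within 180 days, so the rule for repeats matters as well. The second is consistent handling of deviations. Section 10.5 grants no waivers and requires every deviation to be reported. With up to 15 sites (Section 1.0), the same power setting could be logged as a deviation at one site and not at another.

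**Working it through.** No sample size, error rate or analysis figure is involved. The check compares the two stated power limits and then looks for text that links them.

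**Inputs, both from Section 6.3.1**

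- General list, attributed to the IFU: power from 10 to 30 W.
- Posterior wall near the esophagus: recommended maximum power 40 W, with no lower limit stated.

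**Comparison of the ceilings**

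- Difference: 40 - 30 = 10 W.
- Relative to the general ceiling: 10 / 30 = 33%.
- Settings that satisfy both lists: 10 to 30 W.
- Settings above the general ceiling but inside the posterior-wall list: above 30 W, up to 40 W.

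**Search for a link between the two values**

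- Section 6.3.1: the second list is limited by location. The visible text does not say that it replaces, or is an exception to, the general list.
- Source of the 40 W figure: none is visible. The consensus-statement citation belongs to the preceding sentence on minimum contact force.
- Sections 2.2.1 and 3.0: use per IFU or labeling, with no exception by site.
- Section 2.2.5: adds practice guidelines but sets no order of precedence.
- Section 6.2.4: strongly recommends esophageal temperature monitoring, with esophageal deviation as an alternative, and ending energy delivery on a temperature rise. It does not mention power.
- Section 6.4: refers only to the IFU parameters.
- Section 10.5: does not say whether departing from a recommended parameter counts as a deviation.

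The two ceilings therefore differ by 10 W, and no visible passage explains the difference.

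**The case against.** The strongest reply is that the relation is given by location. The later list names its own site, and reading a site-specific list as governing that site is ordinary practice. That is a plausible reading and may be what the sponsor intends. It does not settle the matter, because the plan never states it and Sections 2.2.1 and 3.0 make a general commitment to the IFU without exception.

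The other replies limit the point, and they stand:

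- Both lists are recommendations, and an operator can satisfy both.
- The IFU is not among the documents and may contain its own values for this site.
- A figure is missing directly before the posterior-wall bullets, and Figure 5 is not shown, so linking content there cannot be ruled out.
- The study is observational with only non-powered endpoints (Section 4.0), so no estimate or analysis changes.

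A reader might infer that contact force is contradictory in the same way, since the general entry reads "Contact force (target 20 g, 10-30 g" and the posterior-wall maximum is 15 g. The documents do not support that. A lower force limit at a named site is an ordinary local modification, and the lists cover different places.

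A reader might also infer that Section 6.4 contradicts Section 6.3.1 on repeat procedures. It does not: Section 6.3.1 also starts from the IFU, and its posterior-wall sentences are not expressly confined to initial procedures. What is missing is a cross-reference.

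**Conclusion.** The point holds as a minor wording contradiction with safety relevance. The plan presents 30 W as the upper end of the IFU range and, in the same section, recommends a maximum of 40 W at one site. The gap is 10 W, with neither an explanation nor a source in the visible text.

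This rests on two assumptions: that the text around the missing figure contains no linking statement, and that the general list reports the IFU range correctly.

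A reader might go further and infer that the plan directs use outside the labeling, or that it raises the risk of atrioesophageal fistula. Neither is supported. The first needs the IFU, which is not supplied. The second needs data linking power to event rates, which the documents do not give. No view is taken on which value is right.

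**What to change.** The sponsor and its clinical experts should check both power values against the IFU and reconcile Section 6.3.1 with Sections 2.2.1, 3.0 and 6.4. The revised text should state:

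- which power value governs at the posterior wall near the esophagus, and its source;
- whether the same rule applies to initial and repeat procedures;
- whether power outside the general range at that site is reportable under Section 10.5.

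Sections 2.2.1 and 3.0 need new wording only if the check shows that the posterior-wall value falls outside the IFU.

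The cost is a wording amendment. Sections 10.2 and 12.1 require ethics committee acknowledgement or written approval before it takes effect, at up to 15 sites. It adds no subjects, visits or data.

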## Clinical Investigation Plan

**Figure 5. Persistent Atrial Fibrillation Ablation Strategy**

All subjects will receive ablations to achieve electrical isolation of the PVs. A minimum 20-minute wait period following electrical isolation of all PVs with assessment and documentation of entrance block is recommended per the 2017 Consensus Statement. It is also recommended in the 2017 Consensus Statement that exit block also be demonstrated.

If PV reconnection occurs during or after the wait period following initial PV isolation of all veins, the vein(s) that reconnected and whether it was successfully isolated after administration of additional ablation lesions will be documented on the CRF. Another wait period is not required after performing touch-up ablation lesions for reconnected PVs.

Subjects with a history of AFL, AT or other SVT (spontaneous or induced) or if these arrhythmias are induced at the time of AF ablation, should undergo additional targeted ablation as clinically indicated. All subjects with a history of typical atrial flutter or induced cavotricuspid isthmus (CTI)-dependent atrial flutter need to undergo concomitant AFL ablation and are recommended to have bi-directional block verified by mapping and pacing maneuvers after initial bi-directional block is achieved.

Additional non-PV AF ablation targets (e.g. linear ablation, elimination of CFAEs, rotational activity, autonomic ganglia, isolation of the left atrial appendage, ablation of scar identified by voltage mapping or MRI, and non-PV triggers) are permitted per the investigator’s discretion and will be documented for the trial if sinus rhythm is not restored after isolation of the PVs and ablation of non-PV triggers. If a linear ablation strategy is used, documentation of bidirectional block across the ablation line should be demonstrated and assessed in sinus rhythm and with differential pacing maneuvers. High-dose isoproterenol may be administered to screen for and ablate non-PV triggers. If CFAEs, rotational activity, or non-PV triggers are ablated, the acute goal is elimination of CFAEs, rotational activity, and non-PV triggers and AF termination.

## Clinical Investigation Plan

The goal is that the subject is in sinus rhythm at the end of the procedure. If AF cannot be terminated by ablation at the conclusion of the procedure, it is recommended that the patient be cardioverted and PV isolation rechecked.

It is required to verify that the subject has not experienced pericardial effusion at the end of the procedure.

If for any reason, the subject has the TactiCath SE inserted into their vasculature, but no ablation is performed and the subject will not be rescheduled to receive another ablation procedure, the subject will be followed for 30-days to assess safety and then exited from the trial. Follow-up at 30-days will be conducted via a phone call to the subject (may also be an on-site visit). Subjects who will have their ablation procedure re-scheduled will not need to be re-consented for the trial provided they are rescreened (all eligibility criteria met prior to the procedure) within 90-days of the initial consent date.

### 6.4 Repeat Ablation Procedures

One ablation procedure for treatment of AF/AT/atypical AFL recurrence is allowed during the blanking and therapy consolidation periods (within 180 days post-initial procedure) using the recommended parameters listed in the TactiCath SE *Instructions for Use* document. Note that recurrence and ablation of typical AFL alone does not count as a repeat procedure for AF recurrence.

Certain assessments need to be performed if a repeat ablation is required. Thrombus assessment must be performed prior to ablating the subject. Verification of the exclusion of pericardial effusion must also be performed prior to the conclusion of the procedure.

A 7-day ( $\pm$  2 days) follow-up phone call or in-person visit to the subject will be conducted after the repeat procedure. All other follow-up visits will occur as previously scheduled from the initial ablation procedure. Note that the 90-day blanking period followed by a 90-day therapy consolidation period are still in place from the initial procedure.

